- K: The eDiary will be collected and deactivated for all subjects. For subjects who terminate the study early, the eDiary should be deactivated and collected either on date of early termination or at the Follow-up Visit as applicable. If the Follow-up Visit is conducted remotely, the device should be returned to the site.
- L: Subjects may use the on-demand medication of their choice to treat HAE attacks experienced during the study if that medication has previously been shown to be effective.
- M: Subjects will be dispensed study medication for at home self-administration. Only first administration will be at site.
- N: Subjects will complete the Medication Dosing Diary on the eDiary at Day 1 site visit and then monthly at home through the End of Treatment Visit.

Schedule of Assessments: Treatment Period for All Subjects Under Amendment 1

Study Period		Treatment Period						End of Treatment ^A	Final Visit / Follow-up Telephone Call ^B (2 months after End of Treatment Visit)
Month		12	18	24	30	36	42		
Visit Day		361	541	721	901	1081	1261		
Visit Window (Day) ^C		±4d	±4d	±4d	±4d	±4d	±4d	±4d	-14d
Study center visit		X	X	X	X	X	X	X	
Written informed consent for Amendment 1 and switch to CSL312 200 mg AI ^D		1 st day under Amendment 1							
Physical examination ^E		X	X	X	X	X	X	X	
Vital signs including body weight		X	X	X	X	X	X	X	
SGART and IGART ^F		X		X		X			
TSQM II (subjects ≥ 18 yrs), AE-QoL (subjects ≥ 18 yrs) & WPAI:GH (subjects ≥ 16 yrs) ^G		1 st day under Amendment 1							
Urine collection for urinalysis (central lab) ^H		1 st day under Amendment 1							
Blood Draws (central lab)^I	Hematology / biochemistry / coagulation ^J	X		X		X		X	
	Retention sample for HAE biomarkers ^K	1 st day under Amendment 1							
	Pharmacokinetics / Pharmacodynamics	X	X	X	X	X		X	
	Immunogenicity	X		X		X		X	
Pregnancy test ^L		X	X	X	X	X	X	X	
Review eDiary / assess / document HAE attacks		X	X	X	X	X	X	X	X ^M
eDiary deactivation ^N								X	
Confirm plan for managing potential attack ^O		X	X	X	X	X	X		
IRT CSL312 kit assignment		X	X	X	X	X	X		
CSL312 accountability		X	X	X	X	X	X	X	
Administration of CSL312 ^P		X	X	X	X	X	X		
Concomitant medications and therapies		X	X	X	X	X	X	X	X
Adverse events		X	X	X	X	X	X	X	X

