Abbreviations: AI = autoinjector; HAE = hereditary angioedema; IGART = Investigator's Global Assessment of Response to Therapy; IRT = interactive response technology; NSD = needle safety device; PRO = patient reported outcome; QoL = Quality of Life; SGART = Subject's Global Assessment of Response to Therapy; TSQM II = Treatment Satisfaction for Medication Questionnaire version II; WPAI:GH = Work Productivity and Activity Impairment: General Health; yrs = years.

Footnotes to the Schedule of Assessments: Treatment Period for All Subjects Under Amendment 1

- A: End of Treatment can replace any of the planned site visits (eg Visit Month 36) and should occur 1 month after last dose of CSL312 but no later than September 2025. The End of Treatment Visit may vary per individual subject depending on the end of study in their respective country as per [Section 3.4](#). Any visit beyond Month 36 requires approval from the Sponsor.
- B: Follow-up Visit will be conducted via telephone call only.
- C: Treatment Period visits have \pm 4 day window, with a maximum of 34 days between any 2 doses.
- D: The specific site visit to consent into Amendment 1 and to switch to CSL312 200 mg AI may vary per individual subject. Consent into Amendment 1 and switching to CSL312 200 mg AI may occur starting at the Month 12 Visit. An unscheduled visit to accommodate consent into Amendment 1 and switching to CSL312 200 mg AI (with no other assessments performed at this visit) may be scheduled as needed at dates planned for home doses; this unscheduled visit should be performed according to the dosing schedule. The first administration with CSL312 200 mg AI will always occur at the site. Subjects who decline switching to CSL312 200 mg AI and who have participated in the study for at least 12 months will receive 1 more dose of CSL312 200 mg NSD at the time of the scheduled site visit and subsequently proceed with the End of Treatment Visit 1 month later, as well as a Follow-up Visit 2 months after the End of Treatment Visit, as per the original protocol.
- E: A physical examination will be conducted per the investigator's standard procedure and will also include assessment of unilateral pain and / or swelling of the lower extremities for the purpose of screening for deep vein thrombosis.
- F: Investigator completes IGART in Rave. Subjects complete SGART in tablet.

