2.2.2 Secondary Endpoints

Secondary Objective	Endpoint	Summary Measure(s)
Efficacy Endpoints		
1	Time-normalized number of HAE attacks	The time-normalized number (per month and year) of HAE attacks for the run-in and Treatment period.
1	The reduction in the attack rate during the Treatment Period compared to the Run-in Period	The percentage reduction and the number of subjects experiencing at least $\geq 50\%$, $\geq 70\%$, $\geq 90\%$ or equal to 100% (attack free) reduction in the time-normalized number of HAE attacks on Treatment compared to Run-in Period.
1	The time-normalized number of HAE attacks requiring on-demand treatment	The time-normalized number (per month and year) of HAE attacks requiring on-demand treatment in subjects on treatment.
1	The time-normalized number of moderate and / or severe HAE attacks	The time-normalized number (per month and year) of moderate and / or severe HAE attacks in subjects on treatment.
1	SGART	Number and percentage of subjects rating their response to therapy as good or excellent.

Secondary Objective	Endpoint	Summary Measure(s)
Safety Endpoints		
2	
 • SAEs • Deaths • Related TEAEs • TEAEs leading to study discontinuation • TEAEs by severity • Anti-CSL312 antibodies • Laboratory findings reported as an AE • AESIs (ie, thromboembolic events, abnormal bleeding events, severe hypersensitivity, including anaphylaxis events) • TEAE (for nC1-INH subjects only) 	The number and percentage of subjects experiencing the specified safety events on treatment with CSL312.

AE = adverse event; AESI = adverse event of special interest; nC1-INH = normal C1-esterase inhibitor; SAE = serious adverse event; SGART = Subject's Global Assessment of Response to Therapy; TEAE = treatment-emergent adverse event.

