4.3.3 Procedures for Handling Withdrawals

If a subject is withdrawn from the study, attempts will be made to complete and document the End of Treatment Visit assessments. If the subject is withdrawn from the study after receiving CSL312, every effort will be made to ensure that the relevant safety assessments are completed. The subject may also be asked by the investigator to complete other study assessments.

If the subject withdraws from the study and also withdraws consent for disclosure of future information, the Sponsor may retain and continue to use any data collected before such withdrawal of consent.

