8.6.3.4 Treatment Period: Months 6, 12, and 24 ± 4 days

The following procedures / assessments will be conducted at the Months 6, 12, and 24 site visits:

- Perform physical examination.
- Record vital signs, including body weight.
- SGART / IGART (all ages) (at Months 12 and 24 only).
- TSQM II (subjects ≥ 18 years).
- AE-QoL (subjects ≥ 18 years).
- WPAI:GH (subjects ≥ 16 years).
- Urine collection for urinalysis.
- Collection of blood to assess:
 - Hematology.
 - Biochemistry.
 - Coagulation.
 - Retention sample for HAE biomarkers (adults only).
 - PK / PD.
 - Immunogenicity
- Collect urine for pregnancy test (for women of childbearing potential).
- Review eDiary data and assess / document HAE attacks.
- Confirm access to on-demand HAE medication.

- IRT CSL312 kit assignment.
- CSL312 accountability.
- Record concomitant medications and therapies (type, dose, route, date, and time).
- Record AEs.

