8.6.4.4 Treatment Period: Months 12 and 24 \pm 4 Days

The following procedures / assessments will be conducted at Months 12 and 24:

- Perform physical examination.
- Record vital signs, including body weight.
- IGART / SGART (all ages).
- TSQM II (subjects \geq 18 years).
- AE-QoL (subjects \geq 18 years).
- WPAI:GH (subjects \geq 16 years).
- Urine collection for urinalysis.
- Collection of blood to assess:
 - Hematology.
 - Biochemistry.
 - Coagulation.
 - Retention sample for HAE biomarkers (adults only).
 - PK / PD.
 - Immunogenicity.
- Collect urine for pregnancy test (for women of childbearing potential).
- Review eDiary data and assess / document HAE attacks.
- Confirm access to on-demand HAE medication.
- IRT CSL312 kit assignment.
- CSL312 accountability
- Record concomitant medications and therapies (type, dose, route, date, and time).
- Record AEs.

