- Record AEs

8.6.6.2 End of Treatment Period for All Subjects Under Amendment 1

The following procedures will be conducted at the End of Treatment Visit (1 month after the last dose of CSL312):

- Perform physical examination
- Record vital signs, including body weight
- Collection of blood to assess:
 - Hematology
 - Biochemistry
 - Coagulation
 - PK / PD
 - Immunogenicity
- Collect urine for pregnancy test (for women of childbearing potential)
- Review eDiary data, including investigator assessment of subject-reported symptoms and documentation as HAE attacks or as AEs
- eDiary deactivation (including eDiary collection)
- CSL312 accountability
- Record concomitant medications and therapies (type, dose, route, date, and time)
- Record AEs

8.6.6.3 Follow-up Telephone Contact for All Subjects Under Amendment 1

The following procedures / assessments will be conducted at the Follow-up Telephone Contact (2 months after the End of Treatment Visit):

- Investigator assessment of subject-reported symptoms and documentation as HAE attacks or as AEs
- Record concomitant medications and therapies (type, dose, route, date, and time)

- Record AEs

8.6.6.4 End of Study for All Subjects Under Amendment 1

The treatment period for each subject will be variable. The Sponsor reserves the right to stop the study at any time.

9 Adverse Events

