10.2.1.5 Subject's Global Assessment of Response to Therapy

SGART is a patient-reported outcome that represents the subject's overall response to treatment (Question: Considering all of the ways HAE affects you, please rate your response to the study medication you were given to prevent HAE attacks during this Treatment Period.) using the following ratings:

- none – worse or no response at all, not acceptable,
- poor – very little response, not acceptable,
- fair – some response, acceptable but could be better,
- good – good response, acceptable,
- excellent – excellent response, as good as can be imagined.

The SGART response will be provided via electronic Clinical Outcome Assessment (eCOA) data. Missing answers will not be imputed and will be shown as missing.

The SGART results will be presented descriptively by study visit. The number and percentage of subjects with each rating will be presented. In addition, cumulative responses “Poor or better”, “Fair or better”, “Good or Excellent” will be given. For the percentage for cumulative responses a two-sided 95% CI will be presented. The Friedman test will be used to compare the percentage of subjects with good or excellent responses between study Visit Month 12 and study visits Visit Month 24 and Month 36, respectively, including subjects with assessments for both visits being compared. The tests will be exploratory with an alpha of 5%.

A shift table for SGART will also be provided showing the shift between study visits. For each post-baseline visit, the summary table will show the number and percentages for the following:

- Shift from specific response at previous visit to response at current visit (for example, a shift from poor to fair),
- Any improvement,
- Any worsening of the reported outcome.

The responses to SGART will be listed.

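### SGART and IGART are not collected at the End of Treatment Visit, even where that visit replaces Month 24 or 36, so by-visit response percentages describe only subjects still attending

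*Protocol*

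**What the plan says.** Protocol 2.2.2 makes SGART a secondary endpoint, summarised as "Number and percentage of subjects rating their response to therapy as good or excellent". IGART is exploratory.

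Timing is as follows:

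- **Original protocol, CSL312_3001 and naïve subjects (8.6.3.4):** "SGART / IGART (all ages) (at Months 12 and 24 only".
- **Original protocol, CSL312_2001 subjects (8.6.4.4, covering Months 12 and 24):** "IGART / SGART (all ages".
- **Amendment 1 schedule, row "SGART and IGART ^F":** marked at Months 12, 24 and 36, with nothing under End of Treatment.

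The Amendment 1 End of Treatment list in 8.6.6.2, which opens "The following procedures will be conducted at the End of Treatment Visit (1 month after the last dose of CSL312", contains neither rating. Nor do the two original-protocol lists in 8.6.3.6 and 8.6.4.5.

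Footnote A of the Amendment 1 schedule states: "End of Treatment can replace any of the planned site visits (eg Visit Month 36". For withdrawn subjects, Protocol 4.3.3 says that "attempts will be made to complete and document the End of Treatment Visit assessments"; any other assessment is left to the investigator.

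SAP 10.2.1.5 reports SGART by visit. On gaps it says: "Missing answers will not be imputed and will be shown as missing". It compares Month 12 with Month 24 and with Month 36 in subjects rated at both visits. SAP 10.3.2.1 applies a Friedman test to IGART across Months 12, 24 and 36.

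**The concern.** The SGART question asks about response over the whole Treatment Period, so the end of that period is the natural time to ask it. The plan instead ties the rating to annual visits and omits it from the one visit that every leaver is asked to attend. Footnote A then allows that visit to stand in for an annual visit, and its own example, Month 36, is one that carries the rating.

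What is at stake is the meaning of the good-or-excellent percentage. At each visit it can describe only subjects still in treatment and rated on that day. If subjects leave because the response disappoints them, their view is missing from the result that is meant to show long-term response.

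**Working it through.** **Plan's own figure.** There is none for SGART. The only sample-size statement (Protocol 10.1: 100 subjects, 3%, 95%) reproduces, since 1 − 0.97^100 = 0.952, but it concerns adverse events.

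**Step 1: is the omission part of a pattern?** In the Amendment 1 schedule, hematology/biochemistry/coagulation and immunogenicity are also marked at Months 12, 24 and 36, and both are marked again at End of Treatment. SGART and IGART follow the same annual pattern without the final mark. No reason is given.

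**Step 2: what a replaced visit loses.** Doses fall on Days 1, 31, 61 and so on, and End of Treatment is one month (30 days) after the last dose.

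| End of Treatment falls on | Last dose | Doses given | Rating at that visit |
|---|---|---|---|
| Day 361 (Month 12) | Day 331 | 12 | none planned if End of Treatment stands in |
| Day 721 (Month 24) | Day 691 | 24 | none planned if End of Treatment stands in |
| Day 1081 (Month 36) | Day 1051 | 36 | none planned if End of Treatment stands in |

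Each of these subjects has had the full 12, 24 or 36 months of dosing. The first row is the 12-dose minimum in Protocol 3.2.

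**Step 3: who keeps what.**

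- Stop before Month 12, or End of Treatment displaces Month 12: no planned rating.
- End after a completed Month 12 or 24 visit: earlier ratings kept, final rating absent.
- Decline the autoinjector: rated if the last-dose site visit is Month 12 or 24; no final rating if it is Month 18 or 30.

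**Step 4: does the SAP recover the rating?** SAP 8.2.5 reports by nominal visit without re-allocation and keeps unscheduled data out of summaries. It allows such data to feed an End of Study value, but neither 10.2.1.5 nor 10.3.2.1 defines one for these ratings. A Friedman test needs complete blocks, so a subject without Month 36 leaves the three-visit IGART test.

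**Step 5: size, on assumptions.** Let s be the share who stop unrated, and let stayers rate good or excellent at 95% and stoppers at 50%. These percentages are assumed. With rated subjects as denominator the plan reports 95%. The value for all treated is (1 − s) × 95 + s × 50, so the gap is s × 45 points.

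| s | Rated denominator | All treated, true value | All treated, unrated counted as not good/excellent |
|---|---|---|---|
| 10% | 95% | 85.5 + 5 = 90.5% | 85.5% |
| 20% | 95% | 76 + 10 = 86% | 76% |

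If stoppers rate as stayers do, the gap is zero.

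Bounds that need no assumption about stoppers, for 150 treated and about 95% good or excellent among those rated:

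- 140 rated, 133 good/excellent: 133/150 = 88.7% to 143/150 = 95.3%.
- 125 rated, 119 good/excellent: 119/150 = 79.3% to 144/150 = 96.0%.
- 100 rated, 95 good/excellent: 95/150 = 63.3% to 145/150 = 96.7%.

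**The case against.** Much can be said for the plan. Month 12 carries both ratings in every schedule and planned treatment is at least 12 months, so most subjects should be rated at least once. The investigator may ask a withdrawing subject for further assessments. The paired SGART comparisons and the shift tables are within subject, so a change in who attends cannot by itself create a change between visits. Attrition is shown with reasons in the disposition tables, and early stoppers with at least 30 days of treatment stay in the attack-rate endpoints. No confirmatory test depends on SGART. The one HAE retention figure in the protocol, 36 of 38 completing CSL312_2001 after entering its second treatment period, is a loss of 2/38 = 5.3%. On the same assumed ratings the gap would be 0.053 × 45 = 2.4 points. That is another study, so only indicative.

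These arguments limit the point without removing it. A discretionary exit rating has no defined place in the SGART or IGART analysis. Within-subject comparisons are sound for the subjects they include, but say nothing of those who left.

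A reader might infer that everyone who finishes treatment loses the rating, or that the percentage must drift upward even if response is unchanged. The documents support neither. Finishers normally hold a Month 12 or 24 rating. The upward direction requires both less satisfied stoppers and a denominator of rated subjects, and the SAP states no SGART denominator. With all treated as denominator the error in Step 5 runs downward: 85.5% against 90.5%. Endings caused by country closure or the September 2025 limit are administrative and need not be related to satisfaction.

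**Conclusion.** The gap is real and cheap to narrow. No schedule collects SGART or IGART at End of Treatment, and Amendment 1 lets that visit displace one at which they are due. The by-visit percentages therefore rest on subjects still attending. They overstate response if the denominator is rated subjects and stoppers are less satisfied; where treatment ends for administrative reasons, the main cost is precision.

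The documents give neither a stopping rate nor an expected SGART result, so no size can be established. On the assumptions shown, the overstatement is 4.5 points at 10% stopping and 9 points at 20%. It is smaller at lower loss and nil if stoppers rate like stayers. This weakens the interpretation of one descriptive secondary endpoint and does not touch the primary safety endpoint.

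**What to change.** **Protocol.** Add SGART and IGART to the End of Treatment Visit, including early termination, in all three treatment schedules and in 8.6.3.6, 8.6.4.5 and 8.6.6.2. Where End of Treatment replaces Month 24 or 36, count that rating for the visit.

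**SAP 10.2.1.5 and 10.3.2.1.** State the denominator. Beside the by-visit results, report good or excellent at the last available rating in two ways: among rated subjects, and among all treated subjects with the unrated counted as not good or excellent. Label the second a conservative lower bound, because it is not an unbiased estimate: in the 10% example it misses by 5.0 points downward, where the rated percentage misses by 4.5 upward.

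**Timing.** Footnote A required End of Treatment no later than September 2025, and SAP version 2.0 took effect on 02 Oct 2025. If those visits are finished, only the SAP part applies, and it should be settled before database lock.

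**Cost.** One tablet item and one CRF item at an existing site visit, and one extra table. The reported percentage may become slightly less favourable.

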IRT	Interactive response technology
IV	Intravenous
kDa	kilodalton
mAb	Monoclonal antibody
MedDRA	Medical Dictionary for Regulatory Activities
nC1-INH	Normal C1-esterase inhibitor
NSD	Needle safety device
PD	Pharmacodynamic
PK	Pharmacokinetic
PP	Per protocol
PRO	Patient reported outcome
PT	Preferred term
QoL	Quality of Life
SAE	Serious adverse event
SAP	Statistical analysis plan
SC	Subcutaneous(ly)
SD	Standard deviation
SGART	Subject's Global Assessment of Response to Therapy
SOC	System organ class
TEAE	Treatment-emergent adverse events
TEE	Thromboembolic event
T _{max}	Time to reach maximum concentration in plasma
TP1	Treatment Period 1
TP2	Treatment Period 2
TSQM II	Treatment Satisfaction for Medication Questionnaire version II
WPAI:GH	Work Productivity and Activity Impairment: General Health

List of Conventions

- The abbreviation “C1-INH HAE” is used in this clinical study protocol to include hereditary angioedema type 1 (quantitative decrease in C1-esterase inhibitor plasma concentrations) and hereditary angioedema type 2 (dysfunctional C1-esterase inhibitor present in normal or high plasma concentrations).
- CSL312 has been given the World Health Organization International Nonproprietary Names identification of garadacimab.

1 Introduction

1.1 Background

1.1.1 Factor XII

Factor XII (Hageman factor, FXII) is produced in the liver and is secreted into the plasma; the glycosylated 80 kilodalton (kDa) zymogen circulates with a concentration of ~30 µg / mL and a half-life of 50 to 70 hours [Björkqvist et al, 2014].

Factor XII is the principal initiator of the plasma contact system [Renné et al, 2012]. The contact system is a protease cascade involving the proteins FXII, factor XI (FXI), plasma prekallikrein, and the nonenzymatic cofactor high molecular weight kininogen (HMWK). Upon contact with a negatively-charged surface FXII is converted to activated Factor XII (FXIIa). Several biologic substances have been shown to support FXII activation in vivo, including heparin released from mast cells, misfolded protein aggregates, ribonucleic acid, and platelet polyphosphates [Kenne et al, 2015]. FXIIa triggers fibrin formation through activation of FXI, and also leads to the production of the inflammatory mediator bradykinin (BK) through the kallikrein-kinin pathway. Further cleavage of FXIIa releases the 30 kDa light chain containing the catalytic domain (βFXIIa), which can activate the classical complement pathway. Thus, activated forms of FXII have proinflammatory and procoagulant activities.

1.1.2 Factor XII and the Kallikrein-kinin Pathway

Activation of FXII (to FXIIa) also leads to the production of BK through the kallikrein-kinin pathway. In this pathway, prekallikrein is converted to kallikrein by FXIIa. Kallikrein plays a number of roles. First, it activates FXII zymogens by a positive feedback mechanism to amplify the cascade. Second, kallikrein cleaves HMWK to release the potent inflammatory mediator BK. The binding of BK to BK type 2 receptors activates various intracellular signaling pathways that dilate vessels, induce chemotaxis of neutrophils, and increase vascular permeability and fluid efflux [Björkqvist et al, 2013]. BK production is increased during acute hereditary angioedema (HAE) attacks and is the mediator of swelling in HAE [Nussberger et al, 1998; Nussberger et al, 1999].

